5.0 Evaluation During Study

1. Serum pregnancy test within 10 to 14 days prior to and again within 24 hours prior to the first dose of lenalidomide for Cycles 1, 3, 5, and 7.
2. Baseline:
 - a. Thyroid function tests (TSH and free T4)
 - b. Total cortisol level
 - c. Standard chemistries including AST, ALT, Direct and Indirect Bilirubin, Alk Phos, LDH, Albumin, BUN, serum creatinine, CBC
 - d. For multiple myeloma patients only (within 30 days of registration): SPEP and serum IFE, UPEP and urine IFE, immunoglobulins IgA, IgG, IgM, Beta 2 microglobulin, Serum free kappa and lambda light chain assay. Bone marrow aspiration and biopsy. Bone survey.

3. Before Cycle 1 (if baseline tests and/or exam are > 7 days before start of Cycle 1):
 - a. Standard chemistries including AST, ALT, Direct and Indirect Bilirubin, Alk Phos, LDH, Albumin, BUN, serum creatinine, CBC
 - b. Physical examination and toxicity assessment
 - c. Creatinine clearance. Use Cockcroft-gault formula and ideal body weight (IBW). Use adjusted body weight if >50% over IBW
4. Before Cycles 3, 5, and 7:
 - a. Standard chemistries including AST, ALT, Direct and Indirect Bilirubin, Alk Phos, LDH, Albumin, BUN, serum creatinine, CBC
 - b. Physical examination and toxicity assessment
 - c. Creatinine clearance. Use Cockcroft-gault formula and ideal body weight (IBW). Use adjusted body weight if >50% over IBW
5. Day 14 (+/- 2 days) in Cycles 1, 3, 5, and 7: CBC
6. Before Cycles 2, 4, 6, and 8:
 - a. Thyroid function tests (TSH and free T4)
 - b. Total cortisol level
 - c. Standard chemistries including AST, ALT, Direct and Indirect Bilirubin, Alk Phos, LDH, Albumin, BUN, serum creatinine, CBC
 - d. Physical examination and toxicity assessment (and GVHD assessment in allos)
 - e. Ocular exam to assess for ocular toxicity if clinically indicated.
7. At 1 (+/- 7 days), 3 (+/- 10 days), 6 (+/- 15 days) months, and (+/- 30 days) for months 12, 24, and 36 after last dose of ipilimumab and/or when clinically indicated:
 - a. Physical examination and toxicity assessment.
 - b. Assessment for toxicity (through 30 days after last dose of study drug)
 - c. Assessment for GVHD (in allogeneic patients)
 - d. Thyroid function tests (TSH and free T4)
 - e. Total cortisol level
 - f. Standard chemistries including AST, ALT, Direct and Indirect Bilirubin, Alk Phos, LDH, Albumin, BUN, serum creatinine, CBC

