 - g. Bone marrow aspiration and biopsy, CT scan, PET/CT scan depending on patient's type of hematologic or lymphoid malignancy
 - h. For multiple myeloma patients only: SPEP and serum IFE, UPEP and urine IFE, immunoglobulins IgA, IgG, IgM, Beta 2 microglobulin, Serum free kappa and lambda light chain assay at each visit.
Bone marrow at 1 month follow-up and as clinically indicated.
Bone survey (+/- 30 days) for months 12, 24, and 36 after last dose of ipilimumab and/or when clinically indicated.
8. The International Working Group Response Criteria (Appendix I.) will be used.
9. We will use the International Myeloma Working Group (IMWG) uniform response criteria for multiple myeloma patients. All response categories require no known evidence of progressive or new bone lesions.

International Myeloma Working Group uniform response criteria.

All response categories require two consecutive assessments made at any time.

All response categories require no known evidence of progressive or new bone lesions.

Stringent complete response (sCR) (all of the following):

1. CR as defined.
2. Normal free light chain ratio
3. Absence of clonal cells in bone marrow by immunohistochemistry or immunofluorescence (defined by absence of abnormal k/l ratio of > 4:1 or <1:2)

Complete response (CR) (all of the following):

1. Negative immunofixation in serum and urine.
2. $\leq 5\%$ plasma cells in the bone marrow.
3. Disappearance of any soft tissue plasmacytomas.

Note: While healing of pre-existing bone lesions is not required, no new lytic lesions should appear. Further compression fracture of previously known spine lesion will not be considered as progressive disease.

Very good partial response (VGPR) (one of the following):

1. Serum and urine M protein detectable by immunofixation but not by electrophoresis.
2. 90% or greater reduction in serum M protein plus urine M protein level < 100 mg per 4h.

Partial response (PR) (all of the following):

1. Reduction by $> 50\%$ in serum monoclonal protein.
2. Reduction of urinary monoclonal protein to < 200 mg/24h or $> 90\%$.

Stable disease:

1. Not meeting criteria for CR, VGPR, PR or PD.

Progressive disease (PD) (any one or more of the following):

1. Increase of $\geq 25\%$ from baseline in:
Serum M protein (absolute increase must be ≥ 0.5 g/dL).
Urine M component (absolute increase must be ≥ 200 mg/24h). Only in patients without measurable serum and urine M protein levels.

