Difference between involved and unininvolved FLC levels (absolute increase must be > 10 mg/dL).
Bone marrow plasma percentage (absolute % must be $\geq 10\%$).
2. Definite development of new bone lesions or soft tissue plasmacytomas or definite increase in the size of existing bone lesions or soft tissue plasmacytomas.
3. Development of hypercalcemia (corrected serum calcium > 11.5 mg/dL or 2.65 mol/L) that can be solely attributed to the myeloma.

Relapse from CR (any one or more of the following):

1. Reappearance of serum or urine M protein by immunofixation or electrophoresis.
2. Development $\geq 5\%$ plasma cells in the bone marrow.
3. Appearance of any other sign of progression (i.e., new plasmacytoma, lytic bone lesion or hypercalcemia).

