Kaplan-Meier¹⁰ survival curves will be used to estimate overall survival and progression-free survival. We will also assess the rates of acute and chronic GVHD, other organ toxicity, and secondary immune-based diseases such as arthritis, lupus, and thyroid dysfunction. We will use the method of Gooley et al¹¹ to estimate the cumulative incidence of acute and chronic GVHD with the competing risk of relapse in allogeneic transplant patients. Cox proportional hazards regression analysis will be used to model the association between overall survival and progression-free survival and disease and demographic covariates of interest, including data from the correlative cytokine, immune, and pharmacokinetic studies.

Summary/Cohort Reports

The Principal Investigator is responsible for completing a safety/efficacy summary report, and submitting it to the IND Office Medical Affairs and Safety Group, for review and approval. This should be submitted after the first 3 evaluable patients per cohort, complete 30 days after the last dose of study treatment, and prior to changing dose levels; and every patient per cohort, thereafter.

A copy of the cohort summary should be placed in the Investigator's Regulatory Binder under "sponsor correspondence".

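### Myeloma progression is measured from the pre-treatment baseline, so PR and VGPR patients can lose their whole response and still count as stable, which can only push PFS upward

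*Combined protocol and SAP*

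**What the plan says.** Section 5.0, item 9, adopts named criteria and then writes them out: "We will use the International Myeloma Working Group (IMWG) uniform response criteria for multiple myeloma patients". In the progressive disease list, the level-based items need an increase of at least 25% "from baseline in" serum M protein, urine M component, the free light chain difference or marrow plasma cell percentage. Each has an absolute condition; the serum one reads "Serum M protein (absolute increase must be ≥ 0.5 g/dL".

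Baseline is the work-up in Section 5.0, item 2: "For multiple myeloma patients only (within 30 days of registration): SPEP and serum IFE, UPEP and urine IFE". Nothing in the document refers to a lowest or best value.

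Three other parts of Section 5.0 matter here:

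- Progression can also be called without any M-protein change, for example on "Definite development of new bone lesions or soft tissue plasmacytomas", on growth of existing lesions, or on hypercalcemia.
- Stable disease is the residual category: "Not meeting criteria for CR, VGPR, PR or PD".
- Patients who reached CR have their own relapse list, whose first item is "Reappearance of serum or urine M protein by immunofixation or electrophoresis".

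Section 7.0 says that Kaplan-Meier "survival curves will be used to estimate overall survival and progression-free survival". It does not define a PFS event.

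**The concern.** A patient in PR or VGPR whose M protein climbs back to its pre-treatment value has lost the whole response. Measured against baseline, that patient has a rise of 0%, so no level-based progression item is met. The PR and VGPR definitions no longer apply either, and stable disease is what remains. The deeper the partial response, the more regrowth goes uncounted.

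The document also treats near neighbours differently. A CR patient relapses as soon as M protein reappears on immunofixation. A VGPR patient whose protein is visible on immunofixation but not on electrophoresis is held to 125% of baseline.

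PFS is a secondary objective. It is estimated by Kaplan-Meier and modelled by Cox regression in Section 7.0, so a late progression date enters both analyses. The primary toxicity estimate and the stopping rules are not touched.

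**Working it through.** The plan gives no PFS figure, event count or power statement that depends on this definition, so there is nothing of its own to reproduce. The check compares the serum level at which progression is called under two reference values.

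**Inputs from Section 5.0.** A relative rise of at least 25%, an absolute rise of at least 0.5 g/dL, and follow-up visits at months 1, 3, 6, 12, 24 and 36 after the last ipilimumab dose.

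**Assumptions, not in the documents.** The baseline level, the depth of response, exponential regrowth, and an M-protein doubling time T of 2 to 4 months.

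**Formulas.** For reference value r, progression is called at

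threshold(r) = max(1.25 × r, r + 0.5).

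Delay = T × log2[threshold(baseline) / threshold(lowest)].

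**Direction.** Both terms in the maximum increase with r, and the lowest recorded value cannot exceed baseline. The baseline threshold is therefore never below the other, and the delay is never negative.

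**Main illustration.** Baseline 2.0, lowest 0.2 g/dL (a 90% fall):

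- From baseline: max(2.50, 2.50) = 2.5 g/dL.
- From lowest: max(0.25, 0.70) = 0.7 g/dL.
- log2(2.5 / 0.7) = 1.84 extra doublings.
- Delay: 3.7 months at T = 2, and 7.3 months at T = 4.

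**Other assumed cases:**

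| Baseline (g/dL) | Fall | Lowest | Called at, from baseline | Called at, from lowest | Extra doublings | Delay, T = 2 to 4 months |
|---|---|---|---|---|---|---|
| 3.0 | 75% | 0.75 | 3.75 | 1.25 | 1.58 | 3.2 to 6.3 |
| 3.0 | 55% | 1.35 | 3.75 | 1.85 | 1.02 | 2.0 to 4.1 |
| 1.0 | 55% | 0.45 | 1.50 | 0.95 | 0.66 | 1.3 to 2.6 |
| 0.5 | 55% | 0.225 | 1.00 | 0.725 | 0.46 | 0.9 to 1.9 |
| any | none | = baseline | same | same | 0 | 0 |

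**On the visit schedule.** Progression is recorded at a visit, so put the lowest value at month 1 and count forward. In the main illustration the threshold times are 1 + T × log2(0.7 / 0.2) and 1 + T × log2(2.5 / 0.2).

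- T = 2: 4.6 and 8.3 months, so the recorded visit moves from month 6 to month 12.
- T = 4: 8.2 and 15.6 months, so it moves from month 12 to month 24.
- For baseline 1.0 with a 55% fall and T = 2, the times are 3.2 and 4.5 months. Both are recorded at month 6, so nothing changes.

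**Is the lowest value captured?** The myeloma protein panel is scheduled at baseline and then at the follow-up visits that start 1 month after the last ipilimumab dose. The on-treatment visits (Section 5.0, items 3 to 6) do not list it. With lenalidomide for 21 days, ipilimumab 1 to 3 days later and 4 weeks of rest, the last ipilimumab dose falls at 4 × 22 + 3 × 28 = 172 to 4 × 24 + 3 × 28 = 180 days if every cycle runs on time. A low point in that interval would be recorded only if someone ordered the test.

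**The case against.** The other side has several sound points.

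- **Not every responder is affected.** A reader might infer that all myeloma responders who relapse are called late. The document does not support that. CR patients have a relapse rule that does not use baseline, so they are exposed only if relapse from CR is not a PFS event, which Section 7.0 leaves open. Lesions, plasmacytomas and hypercalcemia also trigger progression at any M-protein level.
- **Many patients may have little to lose.** Autologous patients, 25 of the planned 40, enter within 6 months of transplant without signs of progression. Those with little or no M protein at entry have little or no delay. This does not empty the point: allogeneic patients enter because they are not in CR or have relapsed, so any with myeloma may have disease that can respond and regrow.
- **A reader might infer that PFS is shown to be overstated by some months.** It is not. The months above describe single hypothetical patients, the number of myeloma patients is not given, and PFS events are undefined.
- **A reader might infer that the data for a lowest-value rule are already collected throughout.** They are not, given the gap during the eight cycles.
- **The CR and VGPR asymmetry would narrow but not close.** With a lowest-value reference, a VGPR patient would still need a rise of 0.5 g/dL, while a CR patient relapses on reappearance.

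All of this limits scope and size. None of it changes the fact that the level-based items refer to baseline, or that the resulting error has one direction.

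**Conclusion.** The point holds for myeloma patients in PR or VGPR who had measurable disease at baseline. For them the level-based items can leave a complete loss of response classed as stable disease unless another progression criterion is met. To the extent that PFS uses this progression definition, the estimate can be biased upward and not downward.

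The size for PFS as a whole cannot be computed from the documents. For individual patients, under the assumed levels and doubling times of 2 to 4 months, the delay ranges from zero, where baseline is already the lowest value, to 7.3 months in the main illustration. The scheduled visits can absorb or enlarge it. The effect is confined to a secondary, descriptive endpoint in a pilot safety study, but it comes from a rule the plan states and can be corrected at little cost.

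**What to change.** For the PFS endpoint, measure the 25% rise from the lowest value recorded, at baseline or later, and keep the absolute minimums already listed. In Section 7.0, state that PFS events are progressive disease, relapse from CR, or death.

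Disease progression is also a reason for removal in Section 9.0. The sponsor should state whether that criterion uses the same definition as the endpoint, so that the sections agree.

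The cost is a few lines of text and a slightly less favourable PFS estimate. Because myeloma proteins are not scheduled during the eight cycles, a low value on treatment may be missed. Without added tests, the change reduces the bias but does not fully remove it.

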6.0 Background Drug Information

See package inserts for YERVOY® (ipilimumab) in Appendix E. and REVLIMID® (lenalidomide) in Appendix F.

7.0 Statistical Considerations

Overview

The primary objective of this study will be to assess the safety of lenalidomide alternating with ipilimumab in stem cell transplantation. Patients will receive lenalidomide alternating with ipilimumab for 8 cycles (lenalidomide for 21 days, then one dose of ipilimumab, then repeat lenalidomide 4 weeks later, etc.). The starting and highest allowable dose of lenalidomide in this study will be 10 mg/d. Dose reductions to 5 mg may be allowed within patient based on clinical practice. Ipilimumab is fixed at 3 mg/kg. If the starting combination of lenalidomide 10 mg/d and ipilimumab 3 mg/kg results in toxicity, as defined below in the toxicity monitoring rule, in the first 3 of 3 patients, subsequent patients will be started at a lower combination dose of lenalidomide 5 mg/d and ipilimumab 3 mg/kg.

Secondary objectives include assessing overall response rate, overall survival, progression-free survival, and the cumulative incidence of acute and chronic GVHD with the competing risk of relapse in allogeneic transplant patients.

Safety Monitoring

We expect to accrue a total of 40 transplant patients onto two arms: Autologous (N=25) and allogeneic (N=15). All patients will receive lenalidomide alternating with ipilimumab (L+I). Each transplant arm will be monitored separately using monitoring rules for toxicity. The following stopping rules and boundaries were developed using the Multc Lean Desktop application (version 2.1.0) in the Biostatistics department.

The Principal Investigator and assigned Research Nurse will review the enrolled patients monthly while on active treatment to assess adverse events and stopping rules. The Biostatistician will be consulted as necessary. The data monitoring plan will be provided by the MD Anderson IND Office. This office is responsible to monitor the protocol conduct and data entry.

Toxicity monitoring rules: Each transplant arm (either autologous or allogeneic) will be monitored separately for toxicity. If there is a high probability of observing more than a 30% toxicity rate in either arm, that arm will be stopped. Toxicity for this stopping rule will include the following, at any time during active study treatment, which is defined as the first eight cycles plus 30 days following the last dose of study drug:

- Any grade 4 hematological toxicity at least probably related to study drug that does not resolve within 2 weeks
- Any immune-mediated reaction to ipilimumab that requires permanent cessation of the drug

- Any other grade 3-5 organ toxicity at least probably related to study drug
- (Allogeneic arm only) Any acute grade III or higher GVHD.

Bayesian sequential monitoring⁷ will be employed to perform interim safety monitoring targeting a toxicity rate of not more than 30%. Patients will be monitored in cohorts of 1.

Autologous Arm

For the autologous arm, accrual will be stopped early if

$$\Pr [\text{prob(toxicity)} > 0.30 \mid \text{data}] > 0.975$$

That is, if we determine that there is a greater than 97.5% chance that the toxicity rate is greater than 30% in this arm, then accrual will be stopped. We assume a beta (0.6, 1.4) prior distribution for the toxicity rate, which has a mean of 0.3 corresponding to the 30% target toxicity rate. Stopping boundaries corresponding to this probability criterion are to terminate accrual in autologous patients if

If there are this many (or more) patients in the autologous transplant arm with Toxicity	Stop the arm if this many patients in the arm
3	3
4	4-5
5	5-7
6	6-9
7	7-11
8	8-13
9	9-16
10	10-18
11	11-21
12	12-23
13	13-24
14	ALWAYS STOP

Patients must complete at least two cycles of treatment or have toxicity to be included in the rule. Patients who complete at least two cycles but drop out without experiencing toxicity will be included but not counted as toxicities. If accrual onto this arm is stopped, the study will continue enrolling patients to the allogeneic transplant arm.

The rule will reset at lenalidomide 5 mg if the first 3 of 3 patients at the combination 10 mg lenalidomide dose experience toxicity. If the rule resets after the first three patients, we will continue to enroll up to 25 patients in the autologous arm at the lower combination dose using lenalidomide 5 mg. The Biostatistical collaborator will be consulted as necessary.

The operating characteristics of this rule are shown below.

Table 1. Operating Characteristics for Toxicity Stopping Rule in Autologous Arm

If the true toxicity rate is...	Early Stopping Probability	Achieved Sample Size Percentiles		
		25th	50th	75th
0.1	0.0014	25	25	25
0.2	0.0163	25	25	25
0.3	0.0891	25	25	25
0.4	0.3013	18	25	25
0.5	0.6324	7	16	25
0.6	0.8929	5	9	16
0.7	0.9872	3	5	9

Allogeneic Arm

For the allogeneic arm, accrual will be stopped early if

$$\Pr [\text{prob(toxicity)} > 0.30 \mid \text{data}] > 0.95$$

That is, if we determine that there is a greater than 95% chance that the toxicity rate is greater than 30% in this arm, then accrual for this arm will be stopped. We assume a beta (0.6, 1.4) prior distribution for the toxicity rate, which has a mean of 0.3 corresponding to the 30% target toxicity rate. Stopping boundaries corresponding to this probability criterion are to terminate accrual in allogeneic patients if

If there are this many (or more) patients in the allogeneic transplant arm with Toxicity	Stop the arm if this many patients in this arm
3	3-4
4	5-6
5	7-9
6	10-11
7	12-13
8	14-15
9	ALWAYS STOP

Patients must complete at least two cycles of treatment or have toxicity to be included in the rule. Patients who complete at least two cycles but drop out without experiencing toxicity will be included but not counted as toxicities. If accrual onto this arm is stopped, the study will continue enrolling patients to autologous arm.

The rule will reset at lenalidomide 5 mg if the first 3 of 3 patients at the combination 10 mg lenalidomide dose experience toxicity. If the rule resets after

the first three patients, we will continue to enroll up to 15 patients in the allogeneic arm at the lower combination dose using lenalidomide 5 mg. The Biostatistical collaborator will be consulted as necessary.

The operating characteristics of this rule are shown below.

Table 2. Operating Characteristics for Toxicity Stopping Rule in Allogeneic Arm

If the true toxicity rate is...	Early Stopping Probability	Achieved Sample Size Percentiles		
		25th	50th	75th
0.1	0.0016	15	15	15
0.2	0.0210	15	15	15
0.3	0.0998	15	15	15
0.4	0.2780	14	15	15
0.5	0.5367	7	12	15
0.6	0.7866	3	7	12
0.7	0.9406	3	5	7

Primary Objective

We will estimate the toxicity rate in each arm along with a corresponding 95% credible interval. In addition, toxicity will be summarized by arm, type, and grade.

Secondary Objectives

For secondary objectives, we will estimate response at the end of eight cycles and overall with a 95% confidence interval. We will also estimate specific response types such as humoral and cellular. This data will be used to inform future studies using higher dose combinations. With 15 patients assigned to a transplant arm, if the response rate is 20%, an asymptotic 95% confidence interval will be (0, 0.402). With 25 patients assigned to a transplant arm, if the response rate is 20%, an asymptotic 95% confidence interval will be (0.043, 0.357).

Kaplan-Meier¹⁰ survival curves will be used to estimate overall survival and progression-free survival. We will also assess the rates of acute and chronic GVHD, other organ toxicity, and secondary immune-based diseases such as arthritis, lupus, and thyroid dysfunction. We will use the method of Gooley et al¹¹ to estimate the cumulative incidence of acute and chronic GVHD with the competing risk of relapse in allogeneic transplant patients. Cox proportional hazards regression analysis will be used to model the association between overall survival and progression-free survival and disease and demographic covariates of interest, including data from the correlative cytokine, immune, and pharmacokinetic studies.

Summary/Cohort Reports

The Principal Investigator is responsible for completing a safety/efficacy summary report, and submitting it to the IND Office Medical Affairs and Safety Group, for review and approval. This should be submitted after the first 3 evaluable patients per cohort, complete 30 days after the last dose of study treatment, and prior to changing dose levels; and every patient per cohort, thereafter.

A copy of the cohort summary should be placed in the Investigator's Regulatory Binder under "sponsor correspondence".

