4.0 Treatment Plan

Eligible patients will receive lenalidomide alternating with ipilimumab for 8 cycles.

Patients who are still receiving or just finished (i.e., within 3 months) the original treatment plan will be re-consented to receive 4 additional cycles (i.e., 8 total cycles).

Lenalidomide will be given daily for 21 days (Cycle 1). One dose of ipilimumab (Cycle 2) will be given within 1-3 days from the last day of lenalidomide, then followed by 4 weeks of rest.

Repeat lenalidomide daily for 21 days (Cycle 3) followed by one dose of ipilimumab (Cycle 4) within 1-3 days from the last dose of lenalidomide. Treatment will be repeated for a total of 8 cycles.

Creatinine Clearance (mL/min)	Cycles 1, 3, 5, 7	Cycles 2, 4, 6, 8
Greater than 60	Lenalidomide 10 mg PO daily for 21 days	Ipilimumab 3 mg/kg IV x 1 dose (given 1-3 days after lenalidomide, then followed by 4 weeks of rest)
30 to 60	Lenalidomide 5 mg PO daily for 21 days	Ipilimumab 3 mg/kg IV x 1 dose (given 1-3 days after the last dose of lenalidomide)

Creatinine clearance. Use Cockcroft-Gault formula and ideal body weight (IBW) as described above in inclusion criteria (Section 3.1)

If the starting combination of lenalidomide 10 mg/day alternating with ipilimumab 3 mg/kg results in toxicity in the first 3 of 3 patients (as defined in toxicity monitoring rule) then subsequent patients will be started at a lower combination dose of lenalidomide 5 mg/day (or 5 mg every other day for creatinine clearance of 30 to 60 ml/min) and ipilimumab 3 mg/kg.

4.1 Management of Immune-Mediated toxicity from ipilimumab:

There are no dose reductions for Ipilimumab. The only modifications to drug are to pause until improvement or stop.

Signs and Symptoms	Assessment of cause and severity	Procedure for adverse effects	Ipilimumab therapy
Gastrointestinal Colitis, diarrhea, blood in stool and/or abdominal pain	Exclude other causes (disease progression, GVHD, infection) Measure AE severity using NCI-CTCAE v3.0 (diarrhea/colitis severity grading scale 3)	Mild (grade 1,2): - Symptomatic therapy	Continue therapy
		Mild (grade 2) with longer term symptoms (5-7 days): - Corticosteroid therapy with prednisone 1 mg/kg/day (or equivalent)	Pause therapy until improvement to ≤ grade 1 STOP
		Symptom improvement: taper drug over 4 weeks	
		Severe (grade 3,4) or no improvement after 5 days on steroid (grade 2) or relapse after steroid taper: - Methylprednisolone 2 mg/kg/day IV	
		Symptom improvement: taper drug over 4 weeks	

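### Three toxicities in the first three patients stops the arm in both boundary tables but restarts it at 5 mg in the text, and Tables 1 and 2 leave the restart out

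*Combined protocol and SAP*

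**What the plan says.** Section 7.0 monitors each arm separately, in cohorts of 1, with a beta(0.6, 1.4) prior. An arm stops when the posterior probability that toxicity exceeds 30% is above 0.975 (autologous, N=25) or 0.95 (allogeneic, N=15). The boundary table headed "If there are this many (or more) patients in the autologous transplant arm with Toxicity" has a first row that stops the arm at 3 toxicities in 3 patients. The first row of the allogeneic table stops at 3 toxicities in 3 to 4 patients.

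Under each boundary table the plan adds: "The rule will reset at lenalidomide 5 mg if the first 3 of 3 patients at the combination 10 mg lenalidomide dose experience toxicity". Enrolment then goes on: "we will continue to enroll up to 25 patients in the autologous arm at the lower combination dose using lenalidomide 5 mg", and for the other arm "we will continue to enroll up to 15 patients in the allogeneic arm at the lower combination dose using lenalidomide 5 mg". Section 4.0 gives the same instruction for treatment ("then subsequent patients will be started at a lower combination dose of lenalidomide 5 mg/day"), and the Section 7.0 overview repeats it.

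Directly after each reset paragraph comes "The operating characteristics of this rule are shown below", followed by Table 1 or Table 2. The primary analysis reads: "We will estimate the toxicity rate in each arm along with a corresponding 95% credible interval". Expected total accrual is 40.

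**The concern.** The same event, 3 of 3 at the 10 mg start, has two consequences in the plan: stop the arm, or continue it at 5 mg. The reset is probably meant as an exception to the first row, but no sentence says so. The investigator and research nurse apply the rule at monthly reviews, with the biostatistician consulted as needed. The summary report required before a dose-level change does not settle which instruction applies.

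The second problem is the tables. Coming straight after the reset text, they read as properties of the whole rule, reset included. If they omit it, the plan overstates how often, and how early, a toxic arm closes when 5 mg is no safer than 10 mg.

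Two details are also open: whether 25 and 15 at the lower dose include the first three patients, and how patients before and after a reset enter the per-arm toxicity rate.

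**Working it through.** **Inputs (Section 7.0).** Prior beta(0.6, 1.4); threshold 0.30; cut-offs 0.975 (N=25) and 0.95 (N=15); cohorts of 1; stopping probabilities and sample-size percentiles from Tables 1 and 2. The plan gives no toxicity rate for 5 mg. I assume it equals the 10 mg rate p unless stated otherwise.

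**Step 1: the criterion at 3 of 3.** The posterior is beta(3.6, 1.4), and Pr(rate > 0.30) = 0.9762. This exceeds both cut-offs, so the formal criterion and the first table row agree on stopping.

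**Step 2: reproduce the plan's figures.** I used an exact recursion over patients and toxicities, with 3 of 3 as a terminal stop, one dose, and a stop at the last patient not counted as early. All 14 stopping probabilities match to within 0.0001; at p = 0.5 they are 0.6324 and 0.5367, as printed. Removing the 3-of-3 stop gives 0.6243 and 0.5269, which do not match. All Table 1 sample-size percentiles also match.

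One sign needs almost no computing. Table 1 gives a 25th percentile of 3 patients at p = 0.7. An arm can end at 3 patients only through 3 of 3, which has probability 0.7³ = 0.343. If 3 of 3 leads to further enrolment, a sample size of 3 cannot occur.

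**Step 3: add the reset.** Let P be the stated stopping probability and P2 that of the restarted rule, with 3 of 3 kept as a stop at 5 mg. Then

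closure = P − p³ + p³ × P2.

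With 25 or 15 further patients and equal toxicity, P2 = P and the drop is p³ × (1 − P). At p = 0.5:
- Autologous: 0.6324 − 0.125 + 0.125 × 0.6324 = 0.5864.
- Allogeneic: 0.5367 − 0.125 + 0.125 × 0.5367 = 0.4788.

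| True rate p | P(3 of 3) = p³ | Autologous: stated | with reset | Allogeneic: stated | with reset |
|---|---|---|---|---|---|
| 0.3 | 0.027 | 0.0891 | 0.0645 | 0.0998 | 0.0755 |
| 0.4 | 0.064 | 0.3013 | 0.2567 | 0.2780 | 0.2318 |
| 0.5 | 0.125 | 0.6324 | 0.5864 | 0.5367 | 0.4788 |
| 0.6 | 0.216 | 0.8929 | 0.8697 | 0.7866 | 0.7405 |
| 0.7 | 0.343 | 0.9872 | 0.9829 | 0.9406 | 0.9203 |

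The largest drops are 4.6 points (autologous) and 5.8 points (allogeneic), both at p = 0.5.

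**Step 4: the other accrual reading.** If the first three count within 25 and 15, P2 uses 22 or 12 further patients. Closure at 0.5/0.6/0.7 is then 0.583/0.866/0.981 (autologous) and 0.469/0.721/0.900 (allogeneic). The largest drops become 4.9 and 6.8 points.

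**Step 5: sample size, autologous arm.** The 25th/50th/75th percentiles with the reset are the same under either accrual reading:

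| True rate p | Stated | With reset |
|---|---|---|
| 0.5 | 7/16/25 | 10/20/25 |
| 0.6 | 5/9/16 | 7/11/18 |
| 0.7 | 3/5/9 | 6/8/12 |

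**Step 6: maximum accrual.** If the lower-dose patients are additional, the maxima are 25 + 3 = 28 and 15 + 3 = 18, or 46 if both arms reset. If 25 and 15 are arm totals, the maximum is 40.

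**Limits of the reproduction.** Some Table 2 percentiles do not reproduce under the 0.95 criterion even without a reset (at p = 0.6 I get 5/8/14 against the printed 3/7/12), so the percentile argument rests on Table 1. The printed allogeneic boundaries also do not reproduce Table 2, which is a separate matter. Applied literally, they show the same direction: closure at 0.5/0.6/0.7 goes from 0.643/0.852/0.963 to 0.598/0.820/0.950.

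**The case against.** The reset is the more specific provision and appears four times: in Section 4.0, in the Section 7.0 overview and under each boundary table. Reading the first row as overriding it would leave all four statements without effect, and the row still has a use after the restart at 5 mg. The required review before changing dose levels presupposes that such a change is allowed. On this view only a cross-reference is missing.

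Tables 1 and 2 are indexed by a single true toxicity rate, so they can describe only one dose level, and for that they are correct. The computed drops assume that halving the lenalidomide dose does not reduce toxicity. If 5 mg is safer, closing less often is the purpose of the reset. At the 30% target the reset fires 2.7% of the time per arm and means fewer closures at a rate the plan accepts.

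Much of this stands. The likely intent is clear, the effect is modest, and the accrual and reporting points are mostly missing detail. What does not fall away is that the tables are introduced, right after the reset text, as describing this rule, and nothing elsewhere in the plan limits them to one dose level. The instruction to stop or continue also matters most when toxicity is high: a reset has probability 12.5% per arm at a 50% rate and 34.3% at 70%.

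**Conclusion.** The concern holds and should be fixed. The boundary tables and the reset text give different instructions for 3 of 3 at the 10 mg start, and Tables 1 and 2 give the properties of a rule without the reset. With equal toxicity at both levels, the written rule closes a toxic arm less often than stated, by at most 4.6 to 4.9 points (autologous) and 5.8 to 6.8 points (allogeneic) at the tabulated rates. The range reflects the two accrual readings. In the autologous arm, median sample size rises by 2 to 4 patients at true rates of 0.5 to 0.7.

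The size depends on the assumed 5 mg rate, which the plan does not give. The finding that the tables omit the reset does not depend on it.

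**What to change.** 1. In each arm, state that 3 of 3 at the 10 mg starting level triggers the reset and not a stop, and that 3 of 3 at the 5 mg starting level stops the arm. Mark the first row of each boundary table accordingly.
2. Recompute Tables 1 and 2 for the two-stage rule over stated pairs of toxicity rates at the two levels. Alternatively, label them as applying to one dose level without the reset.
3. State whether 25 and 15 include the first three patients, and make the maximum accrual agree (40, or up to 46).
4. If a reset occurs, report the primary toxicity rate within arm by dose level, before and after the reset. Use dose level and not milligrams, because Section 4.0 already starts patients with creatinine clearance of 30 to 60 mL/min at 5 mg before any reset.

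The cost is a sentence or two per arm and either a short recalculation or a table footnote. If the tables are recomputed at equal toxicity, the stopping probabilities at high rates become slightly less favourable.
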